3 STUDY OBJECTIVES AND ENDPOINTS

Table 3-1 Study Objectives and Endpoints

Objectives	Endpoints
Primary	
To evaluate the within-treatment supra-gingival plaque removal efficacy of four manual toothbrushes after a single brushing event (first use).
 
Change from pre- to post-brushing in mean Rustogi Modified Navy Plaque Index (RPI) - overall* (Day 0).
 
Change from pre- to post-brushing in mean Turesky Modified Quigley & Hein Plaque Index (TPI) - overall (Day 0).
 
* all sites assessed

Secondary	

Objectives	Endpoints
To evaluate the within-treatment supra-gingival plaque removal efficacy of four manual toothbrushes after single brushing events, following 7 and 28 days familiarization with the brush.	Change from baseline (Day 0 pre-brushing) to post-brushing in mean RPI and mean TPI - overall (Day 7, Day 28). Pre- and post-brushing mean RPI and mean TPI- overall (Day 7, Day 28).
To evaluate the within-treatment supra-gingival plaque removal efficacy of four manual toothbrushes at the gingival margin and from inter-proximal sites, after single brushing events, following 0, 7 and 28 days familiarization with the brush.	Change from baseline (Day 0 pre-brushing) to post-brushing in mean RPI and mean TPI - gingival margin sites (RPI only); inter-proximal sites (Day 0, Day 7, Day 28). Pre- and post-brushing mean RPI and mean TPI - gingival margin sites (RPI only); inter-proximal sites (Day 0, Day 7, Day 28).
To evaluate the within-treatment supra-gingival plaque removal efficacy of four manual toothbrushes after 7 and 28 days twice-daily brushing.	Change from baseline (Day 0 pre-brushing) in mean RPI and mean TPI - overall; gingival margin sites (RPI only); inter-proximal sites (Day 7 pre-brushing, Day 28 pre-brushing).
Safety	
To assess the safety and oral tolerability of the four manual toothbrushes after first use (Day 0) and over 28 days' use.	TEAEs

This clinical methodology development study will be considered successful if a numerical reduction in supra-gingival plaque levels is observed for each toothbrush after first use (Day 0, pre- to post-brushing), for both clinical measures.

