4 STUDY DESIGN

4.1 Overall Design

This will be a single center, 4-week, randomized, controlled, examiner-blind, four-treatment arm, parallel design, clinical methodology development study to investigate the plaque removal efficacy of marketed manual toothbrushes in healthy, dentate subjects. Changes in plaque level will be evaluated after first brushing, after two further single brushing events (Days 7 and 28) and following 7 and 28 days usage (twice daily brushing with assigned toothbrush treatment).

Supra-gingival plaque levels will be assessed using two established clinical measures: the RPI and the TPI. Subjects will abstain from oral hygiene for a period of 12-18 hours prior to each assessment visit. Subjects with Day 0 pre-brushing mean RPI_{gingival/interproximal} ≥ 0.6 will be stratified by their Day 0 pre-brushing RPI_{gingival/interproximal} score (lower: mean RPI

gingival/interproximal ≥ 0.6 to ≤ 0.8 ; higher: mean RPI_{gingival/interproximal} > 0.8 to ≤ 1) and randomized to study treatment (Visit 2).

The mean RPI_{gingival/interproximal} ≥ 0.6 is calculated based on the 10 areas for inter-proximal & gingival margins (A, B, C, D, F – facial and lingual sites) as follow: RPI_{gingival/interproximal} sum score/number of gingival and interproximal sites.

To standardize oral hygiene practice, eligible subjects will complete a lead-in period (minimum 5 days) prior to Visit 2 during which they will brush with the toothbrush and regular fluoride toothpaste provided.

The safety and oral tolerability of each toothbrush will be monitored after first use and over the 28-day usage period by review of reported TEAEs.

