Single-use brushing studies are often used as screening tools to give an initial indication of cleaning performance. However, it is not unreasonable to expect toothbrushes that perform well after a single brushing to show greater plaque removal with continued use ([Slot et al. 2012](#)). A longer period of 'home use' allows study subjects to familiarize themselves with a new toothbrush and provides a more representative picture of product performance over time. Longer term toothbrushing studies would also be required to investigate gingival health benefits. In this methodology development study, plaque removal efficacy will be investigated after three separate (on-site) single brushing events (without and with a period of familiarization with the subject's assigned study toothbrush):

- Day 0: first use, no familiarization;
- Day 7: 1 week's familiarization;

Property of GSK Consumer Healthcare - Confidential

May not be used, divulged, published or otherwise disclosed without the consent of GSKCH

SP1963/SOP-208661: Template Version: 14 Mar 2019

- Day 28: 4 weeks' familiarization;

and after an extended period of twice daily brushing (7 and 28 days). The 28 day treatment period has been selected to help inform the design of future longer term studies, while facilitating subject visit scheduling for this study.

Clinical efficacy assessments will be performed at a single clinical site by a single dental examiner to eliminate inter-examiner variability. Intra-examiner variability will be monitored by performing repeat clinical assessments for both plaque indices, in randomly selected subjects, across the study period.

Toothbrush efficacy studies typically include a period of abstinence from oral hygiene prior to clinical assessment visits (i) to standardize oral hygiene practice in the study population and (ii) ensure sufficient plaque growth on the tooth for efficacy evaluation. A systematic review of manual toothbrush studies (59 publications) reported 23–25 hours as the most common period of plaque accumulation prior to brushing efficacy evaluation, 12–18 hours was the next most common ([Slot et al. 2012](#)). In this study, subjects will abstain from toothbrushing for 12–18 hours prior to Visits 2–4 to align with other GSK CH brushing studies.

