12.2 Statistical Methods and Analytical Plan

Additional details of the proposed statistical analysis will be documented in the statistical reporting and analysis plan (RAP), which will be written following finalization of the protocol and prior to study unblinding/analysis (as appropriate).

In this study, baseline is defined as the Day 0 pre-brushing mean plaque score for each index (RPI/TPI). Day 7 and Day 28 pre-brushing plaque levels will also be used to assess plaque removal after single brushing events at these timepoints, noting these values may be influenced by treatment used.

Plaque removal efficacy after first use (change from baseline) will be tested under the null hypothesis:

- H_0 : there is no change from the baseline plaque level;
- H_1 : there is a change from the baseline plaque level.

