12.3.5 Secondary Analyses

Secondary outcome variables include change from baseline in:

- Mean RPI_{overall} (Day 7, Day 28)
- Mean TPI_{overall} (Day 7, Day 28)
- Mean RPI_{gingival margin} (Day 0, Day 7, Day 28)
Sites A, B and C will be used for calculations
- Mean RPI_{inter-proximal} (Day 0, Day 7, Day 28)
Sites D and F will be used for calculations
- Mean TPI_{inter-proximal} (Day 0, Day 7, Day 28)
Mesial and distal sites will be used for calculations

Secondary outcome variables will be derived, based on relevant tooth sites, as the primary outcome variables, with the following summaries generated and analyses performed.

Variable Calculation	Timepoint	Type of Analysis
Actual value	Day 0 (pre- and post-brushing)	Summary statistics

	Day 7 (pre- and post-brushing) Day 28 (pre- and post-brushing)	Plot of pre- and post-brushing values for Days 0, 7 and 30 Box plots
Change from baseline [Day 0 (pre-brushing)]	Day 7 (pre- and post-brushing) Day 28 (pre- and post-brushing)	Summary statistics Plot of change from baseline for Days 7 and 30 ANCOVA for within treatment comparisons

Summary statistics (number of subjects, mean, median, SE, SD, minimum, maximum) will be presented for each outcome variable at each assessment time point by treatment group.

For change from baseline calculations, baseline will be the mean Day 0, pre-brushing plaque score; percent change will also be presented and calculated as $100 \times (\text{Value} - \text{Baseline Value}) / \text{Baseline Value}$. This percent change will be calculated from the aggregated mean levels not at the individual subject level.

Actual mean plaque scores (\pm SE) for both indices will be plotted over time by treatment group. Pre-brushing values will be set at the nominal time recorded (Days 0, 7 and 28); post-brushing values will be set at a small nominal time after (Days 0.5, 7.5 and 28.5). Box plots will also be presented for each outcome variable, over time by treatment group

For variables to be formally analyzed to test for a significant change from zero, change from baseline will be analyzed using an ANCOVA model, with treatment as a fixed effect and the appropriate baseline value as a covariate, as per the primary analysis. For TPI analyses, an extra factor will be included for the RPI_{gingival/interproximal} stratification level (lower/higher). Adjusted mean changes, 95% CIs and p values for change from zero will be presented.

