4.5.1 Efficacy (Secondary)

The secondary efficacy endpoints are:

- Mean RPI_{overall} (Day 7 pre- and post-brushing, Day 28 pre- and post-brushing)
- Mean TPI_{overall} (Day 7 pre- and post-brushing, Day 28 pre- and post-brushing)
- Mean RPI_{gingival margin} (Day 0 pre- and post-brushing, Day 7 pre- and post-brushing, Day 28 pre- and post-brushing), defined as mean RPI score for sites A, B and C
- Mean RPI_{inter-proximal} (Day 0 pre- and post-brushing, Day 7 pre- and post-brushing, Day 28 pre- and post-brushing), defined as mean RPI score for sites D and F
- Mean TPI_{inter-proximal} (Day 0 pre- and post-brushing, Day 7 pre- and post-brushing, Day 28 pre- and post-brushing), defined as mean TPI score for mesial and distal sites

Secondary outcome variables will be derived, based on relevant tooth sites, as the primary outcome variables.

Summary statistics (n, missing, mean, SD, SE, median, minimum, maximum) of pre-brushing, post-brushing and change from Day 0 pre-brushing will be presented for each secondary outcome variable at each assessment time point by study product group in the following tables:

- [Table 14.2.2.1.1](#) for mean RPI_{overall}
- [Table 14.2.2.2.1](#) for mean TPI_{overall}
- [Table 14.2.2.3.1](#) for mean RPI_{gingival margin}
- [Table 14.2.2.4.1](#) for mean RPI_{inter-proximal}
- [Table 14.2.2.5.1](#) for mean TPI_{inter-proximal}

Change from baseline of secondary efficacy variables will be analyzed using ANCOVA model with product group as a fixed effect and the appropriate baseline value as a covariate, as defined below:

- For mean RPI_{overall}: baseline mean RPI_{overall}
- For mean TPI_{overall}: baseline mean TPI_{overall} and RPI stratification level (lower/higher)
- For mean RPI_{gingival margin}: baseline mean RPI_{gingival margin}
- For mean RPI_{inter-proximal}: baseline mean RPI_{inter-proximal}
- For mean TPI_{inter-proximal}: baseline mean TPI_{inter-proximal} and RPI stratification level (lower/higher)

Change from Day 0 pre-brushing to each analysis time points (Visit 2 Day 0 post-brushing, Visit 3 Day 7 pre- and post-brushing and Visit 4 Day 28 pre- and post-brushing) will be summarized for each secondary outcome variable by product group (adjusted mean change, percent change from mean baseline, 95% CIs and p-value for change from zero) in the following analysis tables:

- [Table 14.2.2.1.2](#) for mean RPI_{overall}
- [Table 14.2.2.2.2](#) for mean TPI_{overall}

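### Plaque removal by a single brushing at Days 7 and 28 gets no estimate with a confidence interval, because every planned change is measured from Day 0 pre-brushing

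*Protocol*

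**What the plan says.** Protocol 4.1 sets out two questions beyond first use. Plaque change is to be evaluated "after two further single brushing events (Days 7 and 28) and following 7 and 28 days usage". Protocol 4.2 treats Days 0, 7 and 28 alike: "plaque removal efficacy will be investigated after three separate (on-site) single brushing events".

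Table 3-1 gives two endpoints for overall single-brushing removal at the later visits. One is a change: "Change from baseline (Day 0 pre-brushing) to post-brushing in mean RPI and mean TPI - overall (Day 7, Day 28"). The other is a pair of levels: "Pre- and post-brushing mean RPI and mean TPI- overall (Day 7, Day 28"). The gingival-margin and inter-proximal objective follows the same pattern.

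Protocol 12.2 adds that "Day 7 and Day 28 pre-brushing plaque levels will also be used to assess plaque removal after single brushing events at these timepoints", and notes that treatment may affect those levels. It does not say how they will be used. Protocol 12.3.5 then fixes the reference for all change calculations: "baseline will be the mean Day 0, pre-brushing plaque score; percent change will also be presented".

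In SAP 4.5.1 the summary tables hold three things: "pre-brushing, post-brushing and change from Day 0 pre-brushing will be presented for each secondary outcome variable". The ANCOVA tables report adjusted mean change, percent change, 95% CI and p-value for change from Day 0 pre-brushing at five time points: Day 0 post-brushing, and Days 7 and 28 pre- and post-brushing. The same-visit pre- to post-brushing change appears only in the by-subject listings (SAP 4.4.1.1 and 4.5.1).

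**The concern.** Only at Day 0 is the tabulated post-brushing change the plaque removed by one brushing. At Days 7 and 28 the row in the same position also contains whatever happened to pre-brushing plaque since Day 0. The three post-brushing rows of one table therefore do not measure the same quantity, although the objectives present them as a series of single brushing events.

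Protocol 4.2 expects that brushes which do well after one use may "show greater plaque removal with continued use". A larger Day 28 post-brushing reduction could be read as better removal by one brushing when only the pre-brushing level has fallen. If the pre-brushing level rises, real removal would be understated. The p-value tests the combined change, not the single brushing.

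Drift is possible under this design. The third secondary objective exists to measure it. The lead-in brush is ultra soft, while the study brushes are medium or soft. Subjects are also selected on a high Day 0 pre-brushing RPI, so some regression to the mean may follow. Against this, the 12-18 hour abstinence and a lead-in on the same brushing regimen may keep drift small.

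The study is meant to inform later designs. Sizing a single-brushing study after familiarization requires the SD of the same-visit change, which the planned tables do not give.

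**Working it through.** **1. The plan's own figures.** There is no formal sample size to reproduce. Protocol 12.1 gives about 20 evaluable subjects per group and about 80 randomized: 4 × 20 = 80, which agrees.

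**2. What is estimated.** Count of adjusted estimates in the ANCOVA tables of SAP 4.5.1 (5 variables, 5 time points, 4 product groups):

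| Row type | Count |
|---|---|
| Day 0 post-brushing (same-visit removal) | 5 × 1 × 4 = 20 |
| Days 7 and 28 pre-brushing change from Day 0 | 5 × 2 × 4 = 40 |
| Days 7 and 28 post-brushing change from Day 0 (combined) | 5 × 2 × 4 = 40 |
| Days 7 and 28 same-visit change | 0 |
| Total | 5 × 5 × 4 = 100 |

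Eight of the first 20 (RPI and TPI overall: 2 × 4) are the primary estimates of SAP 4.4.1.2, shown in the same tables.

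**3. What the combined row contains.** For Day 28:

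post28 − pre0 = (pre28 − pre0) + (post28 − pre28)

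The first term is drift over the use period; the second is removal by that brushing.

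**4. Effect on the reported percent.** Let r be same-visit removal as a fraction of that visit's pre-brushing mean, and d the relative fall in mean pre-brushing plaque since Day 0. The planned percent reduction is

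1 − (1 − d)(1 − r) = r + d(1 − r)

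For r, take the 30-53% single-brushing range cited in Protocol 2.1. The documents give no d, so a range is assumed (negative d is a rise):

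| d | r = 30% reads | r = 53% reads |
|---|---|---|
| −10% | 23.0% | 48.3% |
| −5% | 26.5% | 50.7% |
| 0% | 30.0% | 53.0% |
| 5% | 33.5% | 55.4% |
| 10% | 37.0% | 57.7% |
| 15% | 40.5% | 60.1% |

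The fall needed to shift the figure by k points is k/(1 − r). For 5 points: 5/0.70 = 7.1% or 5/0.47 = 10.6%. For 2 points: 2/0.70 = 2.9% or 2/0.47 = 4.3%.

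**5. What can be recovered.** With the same subjects and covariates, ANCOVA is linear in the outcome, so

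adjusted same-visit change = adjusted post-brushing change − adjusted pre-brushing change

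A numerical check agreed to below 1e-15. The point estimate is therefore available by subtraction.

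The standard error is not, because it depends on a correlation that no table reports. For an unadjusted paired change with equal SDs and n = 20, the 95% half-width in units of the common SD is 2.093 × √(2(1 − ρ)) / √20. With ρ assumed:

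| ρ | Half-width (SD units) |
|---|---|
| 0 | 0.66 |
| 0.5 | 0.47 |
| 0.9 | 0.21 |

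Between ρ = 0.5 and ρ = 0.9 the variance factor 2(1 − ρ) goes from 1.0 to 0.2. That is a fivefold difference, and it would carry straight into a future sample size.

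**The case against.** The Day 0 reference is deliberate. It is stated in Table 3-1, Protocol 12.2 and 12.3.5 and SAP 3.1, and Protocol 12.2 gives a reason for caution about later pre-brushing values: treatment may influence them. Protocol 12.2 promises no interval or test for same-visit removal, and the levels it refers to are tabulated with SD and SE and plotted. Effect size is the stated focus, p-values are to be read with caution, and the effect size is available by subtraction. The remark in Protocol 4.2 about continued use can be read as performance over time, which the Day 0-referenced change does address. The same-visit change is not clean either: a brush that lowers pre-brushing plaque leaves less to remove, so it may look worse on that measure.

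Much of this stands. The plan delivers both endpoints in Table 3-1, and SAP and protocol do not contradict each other on the reference value. The Day 7 and 28 pre-brushing change is reported with its own CI, so a careful reader can see the drift. The size of any misreading depends on d, which is unknown. The display list (SAP Attachment 1) was not readable in the copy reviewed, so a same-visit table there cannot be excluded.

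It does not remove the gap. The objectives ask about single brushing events, separately from extended use, and for Days 7 and 28 the text of the plan provides no interval for that quantity. The tabulated SEs cannot supply one. The limits of the same-visit change are a reason to report it beside the pre-brushing change, not to omit it.

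**Conclusion.** The concern holds. As SAP 4.5.1 is written, all 40 Day 7 and Day 28 post-brushing estimates describe extended use and one brushing combined, and no summary or model table gives the paired same-visit change with its SE or CI. The distortion in percent terms is d(1 − r). It is zero without drift and 7.0 or 4.7 points for an assumed 10% fall at r = 30% or 53%, with the same sizes in the other direction for a 10% rise.

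This should be fixed, but it is a gap in reporting and inference for two secondary objectives, not a flaw in the data. By-subject listings would allow the interval to be computed later. The conclusion rests on the body text of the SAP; none of the three changes in SAP Table 5-1 adds such a row or records a decision to leave it out.

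**What to change.** In SAP 4.5.1, add the same-visit pre- to post-brushing change at Days 7 and 28, for the five variables, to the existing summary and ANCOVA tables:

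- Report the adjusted mean, 95% CI and percent of that visit's pre-brushing mean.
- Use the Day 0 baseline as covariate, plus the RPI stratum for TPI, as in the other models. This avoids adjusting for a post-randomization value and keeps the new rows consistent with the planned ones.
- Keep the Day 0-referenced post-brushing change, labelled as the combined effect of extended use and one brushing.
- State that the same-visit change is to be read beside the pre-brushing change, because lower pre-brushing plaque leaves less to remove.
- Record the addition in SAP Table 5-1. If Attachment 1 already lists such a display, refer to it in SAP 4.5.1.

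The cost is SAP wording, one Table 5-1 entry and two extra rows per product group in each table. No new data are needed. The drawback is longer tables and 2 × 5 × 4 = 40 further descriptive estimates on top of 100, with no multiplicity adjustment.

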4 STUDY DESIGN

4.1 Overall Design

This will be a single center, 4-week, randomized, controlled, examiner-blind, four-treatment arm, parallel design, clinical methodology development study to investigate the plaque removal efficacy of marketed manual toothbrushes in healthy, dentate subjects. Changes in plaque level will be evaluated after first brushing, after two further single brushing events (Days 7 and 28) and following 7 and 28 days usage (twice daily brushing with assigned toothbrush treatment).

Supra-gingival plaque levels will be assessed using two established clinical measures: the RPI and the TPI. Subjects will abstain from oral hygiene for a period of 12-18 hours prior to each assessment visit. Subjects with Day 0 pre-brushing mean RPI_{gingival/interproximal} ≥ 0.6 will be stratified by their Day 0 pre-brushing RPI_{gingival/interproximal} score (lower: mean RPI

gingival/interproximal ≥ 0.6 to ≤ 0.8 ; higher: mean RPI_{gingival/interproximal} > 0.8 to ≤ 1) and randomized to study treatment (Visit 2).

The mean RPI_{gingival/interproximal} ≥ 0.6 is calculated based on the 10 areas for inter-proximal & gingival margins (A, B, C, D, F – facial and lingual sites) as follow: RPI_{gingival/interproximal} sum score/number of gingival and interproximal sites.

To standardize oral hygiene practice, eligible subjects will complete a lead-in period (minimum 5 days) prior to Visit 2 during which they will brush with the toothbrush and regular fluoride toothpaste provided.

The safety and oral tolerability of each toothbrush will be monitored after first use and over the 28-day usage period by review of reported TEAEs.

4.2 Rationale for Study Design

Published studies evaluating the plaque removal efficacy of toothbrushes differ widely in design, plaque index, plaque accumulation period, duration and brushing regimen (single use, short and longer-term use) ([Robinson et al. 2006](#), [Slot et al. 2012](#)). The results of this study may inform the design of future plaque removal efficacy studies.

Supra-gingival plaque accumulation will be assessed using two established clinical measures.

- Rustogi-modification of the Navy Plaque Index (RPI) ([Rustogi et al. 1992](#)) which focusses on plaque along the gingival margin and in the inter-proximal areas.
- 6-site Turesky modification of the Quigley and Hein Plaque Index (TPI) ([Lobene et al. 1982](#), [Turesky et al. 1970](#)) which focusses on plaque on the lower gingival third of the tooth surface.

Both scales are descriptive, based on the examiner's subjective assessment of surface plaque coverage. The two measures are strongly correlated ([Cugini and Warren 2006](#)); increasing scores indicate increasing 'severity' (more of the tooth surface covered by plaque). RPI is the more demanding of the two to score, requiring the examiner to make 18 assessments per tooth, compared to 6 for TPI. American Dental Association (ADA) guidelines ([American Dental Association 2016](#)) and a systematic review of powered toothbrush studies ([Robinson et al. 2006](#)) recommend use of the TPI, however, RPI is reported to yield numerically greater pre- to post-brushing differences than the TPI ([Slot et al. 2012](#)). The ability of both measures to characterize the plaque removal capability of the study toothbrushes will be investigated here. Data generated may inform the choice of index in future brushing studies.

Single-use brushing studies are often used as screening tools to give an initial indication of cleaning performance. However, it is not unreasonable to expect toothbrushes that perform well after a single brushing to show greater plaque removal with continued use ([Slot et al. 2012](#)). A longer period of 'home use' allows study subjects to familiarize themselves with a new toothbrush and provides a more representative picture of product performance over time. Longer term toothbrushing studies would also be required to investigate gingival health benefits. In this methodology development study, plaque removal efficacy will be investigated after three separate (on-site) single brushing events (without and with a period of familiarization with the subject's assigned study toothbrush):

- Day 0: first use, no familiarization;
- Day 7: 1 week's familiarization;

Property of GSK Consumer Healthcare - Confidential

May not be used, divulged, published or otherwise disclosed without the consent of GSKCH

SP1963/SOP-208661: Template Version: 14 Mar 2019

- Day 28: 4 weeks' familiarization;

and after an extended period of twice daily brushing (7 and 28 days). The 28 day treatment period has been selected to help inform the design of future longer term studies, while facilitating subject visit scheduling for this study.

Clinical efficacy assessments will be performed at a single clinical site by a single dental examiner to eliminate inter-examiner variability. Intra-examiner variability will be monitored by performing repeat clinical assessments for both plaque indices, in randomly selected subjects, across the study period.

Toothbrush efficacy studies typically include a period of abstinence from oral hygiene prior to clinical assessment visits (i) to standardize oral hygiene practice in the study population and (ii) ensure sufficient plaque growth on the tooth for efficacy evaluation. A systematic review of manual toothbrush studies (59 publications) reported 23–25 hours as the most common period of plaque accumulation prior to brushing efficacy evaluation, 12–18 hours was the next most common ([Slot et al. 2012](#)). In this study, subjects will abstain from toothbrushing for 12–18 hours prior to Visits 2–4 to align with other GSK CH brushing studies.

To ensure study subjects demonstrate the required propensity for plaque formation, only subjects with Day 0 pre-brushing mean RPI_{gingival/interproximal} ≥ 0.6 will be randomized to study treatment (Visit 2). Interproximal and gingival margins were chosen due to the unlikelihood that plaque will be present on the smooth surfaces of the tooth due to contact/rubbing with cheeks and tongue. Subjects will be stratified by their Day 0 pre-brushing RPI score (*lower*: mean RPI_{gingival/interproximal} ≥ 0.6 to ≤ 0.8 ; *higher*: mean RPI_{gingival/interproximal} > 0.8 to 1.0) to ensure treatment groups are balanced for baseline supra-gingival plaque levels.

A systematic review of manual toothbrush studies (59 publications with a total of 212 brushing exercises) reported 30–53% plaque removal after a single brushing occasion (depending on the clinical index used) and concluded that bristle tuft arrangement and duration of use contributed to the plaque removal efficacy of a brush. Four marketed manual toothbrushes with differing brush head designs, and therefore anticipated differences in cleaning performance, have been selected for evaluation. The dental profession typically recommend ≥ 2 minutes brushing at least twice daily for good oral hygiene, however, studies reported in the scientific literature indicate brushing duration to be much shorter (working estimate 45 seconds) ([Gallagher et al. 2009](#)). A 1 minute brushing time has been selected for this study as representative of consumer behavior.

The study toothbrushes differ in visual appearance. The level of blindness for this study is therefore described as 'examiner-blind'. Study toothbrushes will be dispensed by trained site personnel who are not involved in clinical efficacy assessment procedures and used by study subjects in the clinical examination area and the examiner won't be allowed in the room during this period. This will ensure the clinical examiner remains blinded to treatment and so avoid bias in the clinical assessments. Clinical examination and product usage areas will be free from mirrors to minimize the visual impact of disclosed plaque on subject brushing behavior.

Eligible subjects will complete a lead-in period (minimum 5 days) prior to Visit 2, during which they will be provided with a standard flat trim toothbrush and regular fluoride toothpaste (both marketed products) to use in place of their own oral hygiene products. Use of these products will provide the study population with a standardized oral hygiene regimen prior to the Baseline visit and familiarize them with required usage regimen (1 minute timed

brushing, twice daily) and completion of a diary after each brushing. The lead-in period will also serve to wash-out from any anti-bacterial ingredients contained in the subject's own oral care products, in use prior to screening.

